6.2 Primary Data Set

The primary data set to be used to prepare the final analysis and DSMB reports will include data from all eligible patients, regardless of adherence to the protocol. However, since patients receive only a single treatment, adherence to the protocol will only be affected if patients drop out of the study, are lost to follow-up or if patients are seen outside of the visit windows as defined in the study protocol. If a patient withdraws from the study, the Week 48 procedures will be completed where possible.

6.3 Handling Data Irregularities

Data which are missing could impact conclusions drawn from even a small number of patients, and therefore presentations (tabular and graphical) will include an indication of missing values and, where possible, explanations will be provided. All data collected will be reported in DSMB reports. There will be no replacement of missing data and no data will be removed. Data from experimental procedures, or procedures in which individuals are unable to provide reliable results (e.g., poor fixation perimetry), may be presented separately, footnoted, or otherwise indicated in the report.

6.4 Interim Analyses

The DSMB will review accumulating data and evaluate safety of the study prior to escalation to the next dose cohort. No formal interim analyses will be performed prior to dose escalation, but the following section provides analyses that are specific to DSMB reports.

Following completion of Part B of the study, an interim review of data will be conducted on all available safety data and any available preliminary efficacy/activity data up to the three-month time point for patients in the first four cohorts. This review, consisting of descriptive statistics and exploratory figures will be used to provide data to the FDA and IRB/ethics committees before pediatric patients are enrolled in Cohort 5. Formal statistical tests will not be performed as part of the analysis.

6.5 Analyses Specific to DSMB Reports

At a minimum, the DSMB will be provided with the following accumulating data prior to making decisions regarding dose escalation:

- Adverse events and concomitant medications
- Laboratory results
- Humoral antibody response and vector distribution data
- BCVA
- IOP
- Slit lamp examination and fundoscopy data

Note that additional endpoint data may be provided in DSMB reports when available or at the request of the DSMB. Thus, [Sections 7](#) and [8](#) describe analyses and tables/plots (respectively) that will be presented upon final analyses, and at a minimum, those relevant to the above endpoints will be provided in DSMB reports.

6.6 Software to be used for Analyses

Data analyses will be conducted using SAS version 9.2 or higher. Some graphs may be generated in R version 3.2.1 or higher.

7.0 STATISTICAL ANALYSES

In this Phase I/IIa study, statistical analyses will be primarily descriptive and include patient-level reports referred to herein as patient profiles. Although UshStat is applied to only the study eye, where available, ophthalmic results for both the study and fellow eyes will be reported and clearly identified as “study” or “fellow.” Comparisons between the study and fellow eyes could be biased as the two eyes were not randomized to determine which eye received Investigational Product. The following sections describe data presentations which will be available for review prior to proceeding to each cohort and/or at the end of the study. Some variables (primarily ophthalmic variables) may be combined with others in patient profiles. Refer to [Sections 8](#) and [9](#) for sample reports.

Data will be summarized using graphical, tabular and/or listing presentations. In addition to patient profiles, continuous-scaled variables will be summarized by mean and standard deviation and/or median and range while categorical variables will be summarized in frequency tables. Percentages given in the summary tables will be rounded and therefore may not always add up to exactly 100 percent.

The primary analysis time point will be 48 weeks following administration of UshStat, but all results contributing to the primary and secondary endpoints and assessments of safety at all study visits will be presented.

7.1 Patient Flow and Compliance

The number of patients screened for eligibility will be reported in a figure, along with the number deemed ineligible at the Screening (Day -28) visit. The reasons for ineligibility will be provided in footnotes.

A summary of patients’ compliance to the follow-up schedule and study procedures will also be tabulated. The number (%) of patients completing and withdrawing from the study over time along with reasons for withdrawal, including death, by cohort will be presented in tabular format.

7.2 Baseline Characteristics

Baseline demographic and patient characteristics, including height, weight, vital signs, reproductive status, medical history, ocular history, chest X-ray, physical examination findings, ECG, ophthalmic examination findings (including IOP and visual acuity), imaging parameters and laboratory values, obtained from tests given at Screening (Day -28) and Baseline (Day -1) visits will be summarized.

7.3 Primary Endpoint

The primary endpoint is composed of several endpoints related to safety, each of which will be presented at the patient and eye level (refer to [Sections 8](#) and [9](#)). Primary analysis for these endpoints, except adverse events, will compare change from Day -28 to Week 48. Graphical presentation of cohort summaries will also be presented as described, and clinically important changes from Baseline (Day -28) to Week 48 will be indicated and summarized.

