Rationale: definition of baseline was provided to use the data most close to the treatment for more precise evaluation of treatment-emergent safety events and efficacy signals

Other minor changes are also implemented to facilitate operational conduct, clarify or eliminate inconsistencies.

Protocol amendment summary of changes table

Section # and Name	Description of Change	Brief Rationale
Whole document	UshStat / UshStat® replaced with SAR421869	UshStat® was previous name.
DOCUMENT HISTORY	Added, including a table and the sentence stating the amendment is substantial.	Template applied.
OVERALL RATIONALE FOR THE AMENDMENT	Added, for Amendment 8.	Template applied.
Section 17 APPENDICES	Appendix E added: History of protocol amendments. Summary of rationales for previous amendments moved to Appendix E (were at the beginning, before table of contents).	Template applied.
Section 1 SYNOPSIS + Section 6.2 SECONDARY ENDPOINTS + Section 9.3.3 Screening Clinical and Laboratory/Diagnostic Measurements Day -28 + Section 9.3.4 Baseline Clinical Laboratory/Diagnostic Measurements Day -1 + Section 9.3.7 Follow-up Procedures	Secondary (Biological Activity) Endpoints: - 'Contrast sensitivity' added - 'CVAQC (when possible)' added to endpoint 'Visual function questionnaire VFQ 25'.	For better biological activity evaluation.
Section 9.3.11.2 Contrast sensitivity	Additional section (refer to Appendix D).	
Section 17 APPENDICES	Appendix D added: Low-Contrast Sloan Letter Chart Testing.	
Section 9.3.11.11 Visual Function Questionnaire (VFQ-25)	Details on CVAQC added.	
Section 1 SYNOPSIS (Study design, Study dosing schedule, and Study population) + Section 7 STUDY DESIGN + Section 8 STUDY POPULATION	Number of patients in cohorts of Part A and Part B; dose by measured strength added for Part A; number of patients to complete the study.	Additional patients to test additional dose levels based on dilution from the measured batch strength; to provide additional safety information and improve dose selection for Parts B and C.
Section 2 STUDY SCHEDULE	Additional table for Cohorts 3b, 3c, 4, and 5.	Clarification and consistency.
Section 3 STUDY DIAGRAM	Diagram changed.	
Section 4.4 SAR421869 DRUG DEVELOPMENT	Diluent added in components, specification on dilution.	For dilution (measured batch strength).
Section 9.2.4 SAR421869 preparation	One sentence deleted.	Details provided in Pharmacy manual.

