2 STUDY SCHEDULE

2.1 FOR COHORTS 1-3A

	Pre-SAR421869		Days			Weeks					
	-28	-1	0	Day 1	1	2	4	12	24	36	48 ^k
			Surgery		±3 days	±3 days	±3 days	±14 days	±14 days	±14 days	±14 days
Visit Windows	+10 days	-7 days	N/A	N/A							
SAR421869 administration			X								
Entry Criteria	X										
Informed consent/assent	X										
Medical history	X										
Concomitant medication	X	X	X	X	X	X	X	X	X	X	X
Anesthesia assessment	X										
Height	X										
Weight	X										
Vital signs ^c	X	X	X	X	X	X	X	X	X	X	X
ECG	X ^o										
Chest X-ray	X ^o										
Physical examination	X										X
Ophthalmological examination											
BCVA ^a	X	X		X	X	X	X	X	X	X	X
Slit lamp examination	X	X		X	X	X	X	X	X	X	X
Intraocular pressure	X	X		X	X	X	X	X	X	X	X
Fundoscopy	X	X		X	X	X	X	X	X	X	X
Autofluorescence	X						X	X	X	X	X
OCT ^p	X	X		X	X	X	X	X	X	X	X
Perimetry (SKP, GATE, microperimetry) ^a	X ^m	X ⁿ				X	X	X	X	X	X
Fundus photography ^b	X		X	X		X	X		X	X	X
Multifocal and full Field ERG	X								X		X
VFQ-25		X ^o									X ^o
Hematology ^d	X	X ^o		X ^o			X ^o		X ^o		X ^o
Chemistry panel ^e	X	X ^o		X ^o			X ^o		X ^o		X ^o
Kidney function ^f	X	X ^o					X ^o		X ^o		X ^o
Liver function ^g	X	X ^o		X ^o			X ^o		X ^o		X ^o
Coagulation ^h	X	X ^o									

Visit Windows	Pre-SAR421869			Days										Weeks					
	-28	-1	0 Surgery	Day 1	1		2		4		12		24		36		48 ^k		
					±3 days	±3 days	±3 days	±14 days	±14 days	±14 days	±14 days	±14 days	±14 days	±14 days	±14 days	±14 days	±14 days		
Visit Windows	+10 days	-7 days	N/A	N/A															
Urinalysis ⁱ	X	X ^o			X ^o					X ^o			X ^o				X ^o		
Blood for PCR	X			X ^j	X	X	X	X	X	X	X	X	X	X	X	X	X	X	
Blood for Immunology			X ^o							X	X	X	X	X	X ^q	X ^q			
Urine for PCR	X			X ^j	X	X	X	X	X	X	X	X	X	X	X	X	X	X	
Urine pregnancy test	X ^o	X ^{o,l}								X ^o	X ^o								
Adverse events	X	X	X	X	X	X	X	X	X	X	X	X	X	X	X	X	X	X	

Notes:

- a. BCVA, Semi-automated Kinetic Perimetry (SKP), full field German Adaptive Thresholding Estimation (GATE) static perimetry and microperimetry will be performed 3 times during screening period; once at the screening visit (Day -28) and on two occasions at baseline (Day -1).
- b. A photomontage will be taken at the screening visit and Week 48 only.
- c. Vital signs: blood pressure (BP, lying down), heart rate (HR) and temperature taken and recorded before SAR421869 administration. Following surgery vital signs will be measured every 30 minutes for one hour. Vital signs will be obtained on all subsequent follow-up visits.

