6 ENDPOINTS

All patients enrolled into this study will be followed for one year. For all endpoints with repeated measures, the primary time point will be considered the 12-month visit unless otherwise specified. BCVA and perimetry measurements are subject to broad intra-individual variability therefore the baseline value used for these measures will be an average of all the values obtained before surgery. For all other endpoints - last available measures before surgery will be considered as baseline value.

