6.1 PRIMARY ENDPOINT

The incidence of adverse events over a 12-month period following a single intraocular dose of SAR421869.

Clinically important changes from baseline (Day -28) in the following safety assessments:

- Best-corrected visual acuity (BCVA).
- Slit lamp examination.
- Indirect ophthalmoscopy.
- Fundus photography.
- Intraocular pressure (IOP).
- Optical coherence tomography (OCT).
- Laboratory parameters.
- Vital signs.
- Concomitant medications.
- Physical examinations.

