9.3.3 Screening Clinical and Laboratory/Diagnostic Measurements Day -28

The following assessments are required 28 (visit window +10 days) days prior to administration of SAR421869.

- Entry criteria.
- Informed consent/assent.
- Medical history.
- Anesthesia assessment.
- Height.
- Weight.
- Vital signs.
- ECG (not unless clinically indicated in <18 years old).
- Chest X-ray (not unless clinically indicated in <18 years old).
- Physical examination.
- Ophthalmological examination:
 - BCVA (procedure to be performed up to three times in total at screening, once at this visit),
 - Contrast sensitivity,
 - Slit-lamp examination,
 - Intraocular pressure (IOP),
 - Fundoscopy,
 - Autofluorescence,
 - ERG (multifocal and full field),
 - OCT including an infra-red imaging montage,

- Semi-automated Kinetic Perimetry (SKP) full-field German Adaptive Thresholding Estimation (GATE) Static Perimetry and Microperimetry (procedures to be performed up to three times in total during screening, at least once at this visit),
- Fundus photography – including a photomontage.
- Clinical laboratory samples.
- Urinalysis.
- Pregnancy test (not unless clinically indicated in <18 years old).
- Blood for PCR.
- Urine for PCR.
- Adverse events.
- Concomitant medications.

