9.3.6 Surgery

The following assessments are performed on the day of surgery:

- Fundus photography will be performed in the operating room during surgery. This will be post bleb placement and will record the position of the bleb relative to the retinal anatomy.
- Where available, the following assessments will be performed:
 - Surgery video-recording,
 - and/or intra-operative OCT.
- Vital signs 30 and 60 minutes after surgery
- Blood and where possible urine for PCR 60 minutes after surgery.
- Adverse events.
- Concomitant medications.

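### SAP 7.3 measures primary change from Day -28, but protocol Section 6 sets the last pre-surgery value, or the pre-surgery mean for BCVA and perimetry, as baseline; the 2019 memo does not settle it

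*SAP*

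**What the plan says.** **SAP.** Section 7.3 sets the rule for the primary safety endpoints other than adverse events: "Primary analysis for these endpoints, except adverse events, will compare change from Day -28 to Week 48". The same section, SAP 5.1 and the text for Figure 3R in SAP 8.3.2 all equate baseline with Day -28.

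**Protocol.** The opening paragraph of Section 6 says of BCVA and perimetry that "the baseline value used for these measures will be an average of all the values obtained before surgery". It continues: "For all other endpoints - last available measures before surgery will be considered as baseline value". The Amendment 8 rationale presents this as a correction: "definition of baseline was provided to use the data most close to the treatment for more precise evaluation". Yet protocol 6.1, directly below, still reads: "Clinically important changes from baseline (Day -28) in the following safety assessments". The synopsis gives the same endpoint with no day attached.

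**2019 memo on the final tables.** It names SAP version 2 of 22 July 2016 as the approved version. Amendment 8 was signed in August 2018. The memo replaces the table list and the adverse event shells. Its titles for Tables 3M and 3N refer to pre-surgical values and that for Table 3LL to baseline, and it defines neither term. The titles of Table 3O and Figures 3Z and 3AA name no reference value.

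**The concern.** A programmer who follows SAP 7.3 and one who follows protocol Section 6 would use different readings for the same patient. The change summaries are the trial's main quantitative ophthalmic safety output, and the memo's adverse event shell shows three patients per cohort. One altered baseline can therefore move a cohort mean visibly, and one reclassified eye moves a cohort percentage by 33 points (1/3). Amendment 8 was meant to bring baseline closer to treatment. The SAP rule takes the earlier of the two scheduled pre-surgery visits.

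**Working it through.** The plan gives no sample size, power or SD, so there is no figure to reproduce. The check is textual, followed by an illustration of size.

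**1. Do the two rules pick different readings?** From the schedules in protocol 2.1 and 2.2 and from 9.3.4:

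| Measure | Day -28 | Later pre-surgery reading | Baseline named in its own SAP section |
|---|---|---|---|
| IOP | yes | Day -1 | none (7.3.4) |
| Slit-lamp and fundoscopy grades | yes | Day -1 | Day -28 to Week 48, apparently an observation window (7.3.3) |
| OCT | yes | Day -1 | none (7.3.5) |
| Laboratory, Cohorts 1 to 3a | yes | Day -1, except fasting glucose and cholesterol (screening only) | none (7.3.6) |
| Vital signs | yes | Day -1, possibly Day 0 | none (7.3.7) |
| BCVA | once | twice at Day -1 | none in 7.3.2; average in 5.1 |

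Where the specific section is silent, 7.3 governs and takes a reading scheduled 27 days before the Day -1 visit. Re-screening (protocol 9.3.5) can widen the gap. For vital signs, footnote c of the schedule has them "taken and recorded before SAR421869 administration", while protocol 9.3.6 lists for the day of surgery only "Vital signs 30 and 60 minutes after surgery". The documents therefore leave open whether a Day 0 reading is the last one before surgery.

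**2. Which final outputs carry a change?** In the memo list: IOP (Table 3N, Figure 3AA), inflammation (Tables 3Q to 3S), vital signs (Table 3LL), laboratory values (Table 3DD) and BCVA (Tables 3M and 3O, Figure 3Z). OCT and perimetry have listings and by-patient figures only.

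**3. Size, one reading per visit.** Let s be the error SD of one reading (not in the documents), with independent errors and no true change before surgery.
- SD of change is s·√(1+1) under either rule, so the noise is equal.
- The two baselines differ with SD s·√2 = 1.41s per patient, and 1.41s/√3 = 0.82s for a three-patient mean.
- IOP, assuming s = 1 to 3 mmHg: 1.4 to 4.2 mmHg per patient and 0.8 to 2.4 mmHg per cohort mean.

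**4. Size for BCVA, only if 7.3 is applied literally.** Protocol 9.3.3 allows fewer than three readings: "procedure to be performed up to three times in total at screening, once at this visit". Baseline error variance in units of s²:
- three independent readings: 1/3;
- three readings with error fully shared within Day -1: (1+4)/9 = 5/9;
- two readings, one per visit: 1/2.

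The error SD of change from one Day -28 reading, relative to change from the mean, is √(2/(4/3)) = 1.22, √(2/(14/9)) = 1.13 and √(2/(3/2)) = 1.15. It is 13% to 22% larger with three readings and 15% larger with two. Adding true between-patient variation of SD s brings this to 8% to 13%; with SD 2s it is 4% to 6%.

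The candidate BCVA baselines differ with SD √(6/9) = 0.82s, √(8/9) = 0.94s and √(1/2) = 0.71s respectively.

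**5. Table 3O (illustration).** The memo gives no cut-off. Simulation used 2,000,000 normal draws, mean true change 0, s = 2, 4 or 6 letters, true-change SD 5 or 10 letters, and 9 study eyes. Expected eyes classified differently:

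| Cut-off | Change in either direction | Losses only |
|---|---|---|
| 10 letters | 0.30 to 1.96 | 0.15 to 0.98 |
| 15 letters | 0.04 to 1.27 | 0.02 to 0.64 |

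**The case against.** The strongest reply is that SAP 7.3 matches the protocol's own primary endpoint section, so the SAP inherited a contradiction rather than made a choice. That is fair about the origin. Calling the label in 6.1 a leftover is an inference, though a well-supported one: Amendment 8 lists only the first paragraph of Section 6 for this change, and the synopsis has no Day -28. It does not rescue 7.3, because two incompatible rules remain and no passage ranks them.

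Second, the final titles never say Day -28, and the Figure 3R text that does is not on the memo's list. SAP 7.2 attaches the word baseline to Day -1, so Table 3LL could be read correctly. This stands as a possible reading, but undefined titles do not override an explicit rule in 7.3.

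Third, a reader might infer that every final ophthalmic change table is affected. The documents do not support that. The memo lists no OCT or perimetry change table; the perimetry conflict lies in SAP 7.4 and 7.4.1. For BCVA, SAP 5.1 uses the screening-period average and the patient profile footnote in SAP 9.1 also averages, which largely agrees with protocol Section 6. The Table 3O counts therefore depend on a literal reading of 7.3 as well as on assumed SDs and cut-offs.

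Fourth, the study is descriptive, with results at all visits presented. That limits the harm, and it stands. One gap is that the patient profile omits the first screening BCVA, so change from Day -28 cannot be read there.

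**Conclusion.** The SAP is wrong as written on baseline, and nothing later corrects it. The firm effect is on change summaries for IOP, inflammation grades, vital signs and Cohort 1 to 3a laboratory values other than fasting glucose and cholesterol. The two rules differ there with SD 1.41s per patient and 0.82s per three-patient mean, assuming independent errors of equal size. OCT change is affected under SAP 7.3 and 7.3.5 but has no final change table. BCVA outputs are affected only under a literal reading of 7.3.

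Absolute IOP flags and laboratory flags set against the upper limit of normal do not change. The flag for an inflammation change of two or more steps can change, but probably rarely, since pre-existing uveitis in the study eye is an example of an exclusion. A reader might infer that all adverse event tables are untouched. That goes too far: the ocular AESI criterion for visual acuity loss (protocol 11.5) and the ALT criterion (protocol 11.6.3, Table 4) both refer to baseline.

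A reader might also infer that the trial's safety findings are invalid. The documents do not support that: no formal test depends on the baseline and the underlying data are unchanged. This should be corrected before the final tables are produced.

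**What to change.** - Add one baseline definition to the SAP or the memo that applies protocol Section 6: mean of all pre-surgery values for BCVA, SKP, GATE and microperimetry; last pre-surgery value for every other endpoint. State whether Day 0 pre-administration vital signs count.
- Use it in place of Day -28 in SAP 5.1, 7.3, 7.4, 7.4.1 and 8.3.2, and in 7.3.9 where the physical examination is repeated at re-screening.
- Apply it to Tables 3M, 3N, 3O, 3Q to 3S, 3DD and 3LL and Figures 3Z and 3AA, and to the AESI criteria that refer to baseline.
- In SAP 7.3.3 keep Day -28 to Week 48 as the observation window, and state that the step change is measured from this baseline.
- Reconcile protocol 2.2, which shows Day -1 blood tests in Cohorts 3b to 5 only at re-screening, with 9.3.4, which lists them without a cohort limit.
- Remove the Day -28 label from protocol 6.1 at the next amendment.

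Measures taken before surgery only at Day -28 need no change: ERG, autofluorescence, pre-operative fundus photography, fasting glucose and cholesterol, and the physical examination unless repeated.

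The cost is one definition and one derived variable, with no new data. The protocol wording needs a formal amendment (protocol 15.8) and can wait for the next one.
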